### **Ethical issues, safeguarding and serious adverse events**

Ethical approval for the study will be obtained from the London School of Hygiene & Tropical Medicine (LSHTM) Research Ethics Committee. Any member of the research/fieldwork team working with students without supervision by school staff will be required to have a full disclosure and barring services check. All work will be carried out in accordance with the research ethics framework laid down by the Economic and Social Research Council and the General Data Protection Regulation 2016. Data processing will operate on the basis of the public task legal basis.

Head teachers as gatekeepers will be asked for informed consent for random allocation and intervention. We will liaise with LSHTM ethics committee during the adaptation phase to determine if it will approve an approach to students' participation in research activities consisting of students' informed active (opt-in) written assent and parents' passive consent (whereby parents would be sent written information about the research and have the right to opt out their children if they wish). Parental opt-in consent is not a legal requirement for non-medical research with children of primary school age. We are aware of a number of trials of public health interventions conducted in primary schools which have used opt-out parental consent. Informed by our review of the law and guidance on research ethics and school-based studies, we anticipate that this is a viable option for our study. However, if we are instructed by our ethics committee that parental opt-in consent is required, we will examine in the adaptation phase the most appropriate means to maximise parental responses to this, for example via using multiple communication routes including parental meetings, attending parents' evening and electronic communications.

In all cases of data collection, adult participants and the parents of students will be given via an information sheet one week before data collection and will be able to opt themselves/their children out of this should they wish. Just before data collection, adult participants who have not previously opted or been opted out will receive a plain English, written description of the study. Student participants will receive an oral description of the study and process, and chance to ask questions of trained fieldworkers just before data collection. This process of providing oral information to students and obtaining verbal assent from students will be witnessed by a member of school staff or another independent observer. Participants will be advised that participation is voluntary and they may withdraw at any point or not answer questions which they do not wish to. All participants will be advised that they are free to withhold consent and this will not be communicated to others within the school or family. Participants will then be asked for their written consent (or, in the case of students, assent) to participate. Students opting not to participate in research activities will continue with normal school activities.

All participants will be informed in consent materials that the information they provide will be treated with anonymity and confidentiality, as well as the circumstances in which we would need to breach confidentiality. With Place2Be, we will develop standard operating procedures for dealing with safeguarding concerns. We will define age-appropriate defined

categories of abuse reported through the research that would necessitate our breaching confidentiality to ensure individuals are offered care and protection, informed by existing clinical guidelines. We will ensure balance between our ethical duty of promoting participant autonomy and wellbeing. Where defined categories of abuse are indicated in questionnaires, we will contact the safeguarding lead in the school. Where these are reported directly to research staff during data collection, we will discuss with the student that there is a need for a response prior to contacting the school safeguarding lead. In each school, a senior member of staff will be identified who is not directly involved with the intervention and to whom staff or students may go if they have complaints about any elements of the intervention or research.

Interviews, focus groups and observations will not aim to explore personal experiences of bullying or mental health problems. In the case of focus groups, our researchers will be trained to ensure that discussions do not move in the direction of personal disclosures since this is not the purpose of the groups and it would be very difficult to ensure that other participants do not communicate such disclosures outside the group. However, if participants in interviews or focus groups describe any abuse, bullying or mental health problems they have experienced, or become upset in any way, our researchers will be trained in how to respond. In interviews, researchers will stop the interview and determine the need for a referral to support within the school. In focus groups, researchers will aim to stop sensitive discussions, and assess the need for individual support at the end or stop the focus group if the assessment is that immediate support is needed.

We will monitor safeguarding concerns and standard categories of serious adverse events via regular consultation with schools. The study steering committee and LSHTM ethics committee will be provided with anonymised reports of safeguarding concerns and serious adverse events, categorised by type, circumstances and the plausibility that these are related to intervention or research activities. Because all follow-ups occur at 12 months, there will be no interim analyses. The study steering committee will consider stopping the pilot RCT if there is any suggestion of an association between the number of safeguarding concerns and serious adverse events plausibly associated with the intervention or trial.

## **SOCIOECONOMIC POSITION AND INEQUALITIES**

Learning Together Primary Schools is a universal intervention which aims to disproportionately benefit disadvantaged and minority students by addressing structural influences on bullying and social and emotional problems, which are likely to be particularly implicated in adverse outcomes among disadvantaged and minority students. These include the experience of school systems and sense of belonging in school. The intervention aims to ensure such students are active participants in intervention planning, and reached by intervention activities such as action groups and restorative practice.

PPIE and research methods will be inclusive for disadvantaged and minority students, for example by using fieldworkers from diverse backgrounds, using plain written English materials and supporting all students who need help in surveys and other data collection. Schools recruited to the adaptation phase will all have high rates of free school meal entitlement (measure of poverty). Schools recruited to the pilot RCT will vary by free school meals and Ofsted rating. The pilot RCT will focus recruitment on south-east England but within this include areas of high and low deprivation. A phase III RCT would be national in focus and aim to be representative in terms of school free school meal entitlement.

In the pilot RCT, we will assess how intervention reach and acceptability vary by student gender, ethnicity, socio-economic disadvantage and school engagement, and by school-level measures of free school meal entitlement. Student recruitment to qualitative research will be purposive by gender and ethnicity. It will not be feasible in schools to purposively

sample students by socio-economic position but we will strive to be inclusive of a diverse range of students. In a phase III RCT, we would examine moderation of intervention effects by student gender, free school meal entitlement (as a marker of socio-economic disadvantage), ethnicity and school engagement to assess impacts on health inequalities.

## **DISSEMINATION, OUTPUTS AND ANTICIPATED IMPACT**

Knowledge exchange will target public health and education policy-makers, school staff and students, and the public. The purpose of dissemination at this stage is to raise awareness of the intervention approach and share findings about its feasibility, rather than to support immediate scale-up. Knowledge exchange is built into the proposed work from the outset via the policy stakeholder group. As well as reporting in the NIHR Public Health Research journal, we will submit at least two open-access papers, and present at the Science Media Centre and two conferences (European Society for Prevention Research; Lancet UK Public Health Science). We will develop plain English research summaries for participating schools, the children's and policy stakeholder groups, and various national and regional school health research networks. We will offer webinars to support this communication. This engagement aims to recognise the contribution of organisations and individuals that we have involved in the pilot RCT, continue the collaboration via two-way communication, and ensure these groups are willing to continue the collaboration into a future phase III RCT. We will draft an article for the Times Education Supplement about the research. We will use social media to increase public awareness. We will present emerging findings at two meetings with policy-makers (including health and social care and education department officials, and public health agencies in the UK nations) and via the Mental Elf website. This is intended to maintain policy interest in the intervention so that policy stakeholders would be supportive of a phase III RCT should this pilot RCT suggests its feasibility. Some of this dissemination activity will continue beyond the pilot RCT period, supported by the work of institutionally funded staff.

Learning Together Primary Schools will be developed as a potentially scalable programme for schools. The most important scientific outputs generated by this project will be increased knowledge about the feasibility and acceptability of delivering and trialling this intervention. This will inform the development of a subsequent proposal to NIHR for a phase III effectiveness trial. Within this effectiveness trial, schools would fund the intervention as they will in the pilot RCT. We will assess in this pilot RCT whether this funding model is likely to remain feasible in the near future. If the phase III trial found the intervention to be effective, this would be scaled up, marketing the intervention to schools, local authorities and school networks. Accreditation for the intervention would then be sought from Blueprints for Positive Youth Development and Early Intervention Foundation to promote scale-up, as it has done with the original Learning Together intervention. As described above, the phase III trial would conduct several analyses of implementation, moderation aiming to inform and contribute to the scalability and transferability of the intervention. Intellectual property newly generated by the study will be held by LSHTM which will grant a license for collaborating institutions and organisations to use this appropriately. Existing third-party intellectual property (restorative practice training materials, survey measures) will be used with permission in this study.

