The review of systematic reviews will address the following questions: (1) are there additional intervention components (including social and emotional skills curricula) that are elements of effective primary school bullying prevention interventions, which are consistent with the theory of change for the Learning Together Primary Schools intervention and which could be feasibly and usefully incorporated into the intervention?; (2) are there factors influencing the feasibility, acceptability, reach or effectiveness of primary school bullying prevention interventions that should be considered in adapting Learning Together for primary schools; (3) are there feasible, acceptable and reliable methods of surveying primary school teachers and students reported in evaluations of primary school bullying prevention interventions that could usefully inform the choice of methods for the pilot trial?; (4) do evaluations of primary school bullying prevention interventions use parental opt-out or opt-in consent?; and (5) do evaluations of primary school bullying prevention interventions suggest any amendments to the proposed methods for the pilot RCT?

The online survey of primary schools in SE England will address the following questions: (1) are the intervention components and methods we propose to include in Learning Together

Primary schools feasible and acceptable to implement in English primary schools?; (2) do English primary schools already deliver any of these components and if so with what training, facilitation or other support?; (3) do English primary schools deliver social and emotional skills curricula and, if so, which ones, comprising how many lessons and targeting which students?; (4) how much would English primary schools be prepared to pay for an effective bullying prevention intervention?; (5) are the evaluation methods proposed for the pilot RCT feasible and acceptable to conduct; and (6) would schools potentially be interested in participating in a pilot or phase III trial of this intervention?

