## **Phase 2: External pilot cluster RCT**

### ***Design overview***

The external pilot cluster RCT will occur in six primary schools (four intervention, two control). Recruitment, baseline surveys of students and teachers, and randomisation will occur in April-July 2024. Schools will be randomly allocated 2:1 to intervention/control (1:1 in phase III RCT) stratified by free school meals (plus Ofsted rating in phase III RCT) in June/July 2024. A 2:1 allocation will allow us to pilot randomisation while ensuring diversity across four schools for intervention piloting. The intervention will be implemented in the four intervention schools from September 2024 to July 2025. The pilot RCT will include an integral process evaluation and economic evaluation feasibility study (figure 2) occurring during this time. Follow-up surveys will occur in June/July 2025. The primary outcome for the pilot RCT will be assessing criteria for progression to a phase III RCT. Primary and secondary outcome measures for a phase III RCT will be assessed for completion and reliability but effects on these outcomes will not be assessed. These outcomes are described in detail below but consist of twin primary outcome measures assessing student-reported bullying victimisation and perpetration in the past two months, plus secondary outcomes consisting of: adult-reported social and emotional problems; student-reported cyber-bullying victimisation; student-reported wellbeing at school; routine data on student attendance/attainment; teacher-reported student behaviour; teacher-reported self-efficacy; and teacher-reported burnout.

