### **Recruitment and randomisation**

We will recruit primary schools in south-east England inclusive of years 3-6. Schools will vary by free school meals (measure of poverty), Ofsted rating (measure of school capacity) and school type so we can assess feasibility across factors likely to affect this. As with our previous trials, schools will be recruited by a combination of emails and phone calls to schools, local authorities, school networks and academy chains. Response rates will be recorded, as will any stated reasons for non-participation.

As explained above, after baselines, schools will be randomly allocated 2:1 to intervention/control (1:1 in phase III RCT) by LSHTM clinical trials unit (CTU), stratified by free school meals (plus Ofsted rating in phase III RCT). A 2:1 allocation in the pilot RCT

will enable us to pilot randomisation while ensuring sufficient diversity of schools in the intervention arm for intervention piloting. Piloting randomisation is necessary given the paucity of UK RCTs of primary school bullying prevention. Schools will be given unique study numbers to preserve allocation concealment within the CTU. The CTU will inform the fieldwork team of allocations who will then inform schools. Informed by the Positive Choices and 'If I Were Jack' RCTs, we will incentivise recruitment and retention by offering a £500 payment to all schools with an additional £1,000 for those allocated to the intervention group, reflecting the greater research load on such schools. Previous studies suggest that payment is now absolutely essential for maintaining school participation in research particularly in the current context of current stretched school budgets and institution strain. Each school will be allocated a named research liaison contact to facilitate retention.

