***Procedures, delivery & dose:*** All staff will undertake restorative practice in their tutor groups and classrooms to prevent conflict and respond to minor incidents coming to their attention. Selected staff will facilitate restorative practice conferences in response to more serious incidents which they identify. The action group will meet termly and: review needs data to decide local priorities; identify staff to be trained; revise rules/policies to support restorative practice; and plan communications to students/parents. The action group will include approx. six staff (diverse by seniority/role) and eight students from years 3-6 (also diverse by gender, ethnicity, school engagement). If it is determined in the adaptation phase that the intervention should involve a curriculum, schools will deliver this in lesson time.

Planned adaptations: Guided by the manual and needs data, schools will identify local priorities re. the forms of bullying to be addressed and the student groups most affected.

Cost: £1500 per school met from sources other than schools for the pilot.

The intervention described above complements existing activities.

The **comparator** will be treatment as usual with schools continuing with existing activities to prevent bullying and student social and emotional problems. Process evaluation will describe this. Initial PPIE suggests that some schools already use restorative practice but few use a whole-school approach or are guided by training/materials.

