#### Economic evaluation data collection

The pilot RCT will examine whether it is feasible to assess cost effectiveness using cost-consequence and cost-utility analyses within a phase III trial. The use of CHU-9D is described above. We will assess the feasibility of estimating costs within the trial period arising from primary and secondary outcomes. Within the pilot, study methods to measure the incremental cost of the intervention in a phase-III trial study will be developed and piloted. With use of a broad public and third-sector perspective, resources to be measured will include: resources used by trainers, Place2Be and schools. Within this, key interventional resources will include Place2Be, L30 Relational Systems and school staff time, training events, meetings and consumables. Measures will include: standardised sessional checklists to monitor and document attendance, preparation and delivery time for key training events, action group meetings and restorative practice meetings (as well as the curriculum if this is part of the intervention); and the completion of surveys and log-books by school staff charged with intervention delivery, assessing time spent on tasks relating to intervention, staff travel and other expenses relating to the intervention charged to a specific project grant code.

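### The protocol contradicts itself on who pays for the intervention in the pilot; on its more specific statement, the pilot does not test the school-funded model it says it will assess

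*Protocol*

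**What the plan says.** Two sections of the protocol say who pays for the intervention during the pilot.

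- Dissemination, outputs and anticipated impact: "Within this effectiveness trial, schools would fund the intervention as they will in the pilot RCT". The next sentence makes a commitment: "We will assess in this pilot RCT whether this funding model is likely to remain feasible in the near future".
- Intervention and comparator, cost line: "Cost: £1500 per school met from sources other than schools for the pilot".

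Three other places bear on the point.

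- Recruitment and randomisation describes participation payments: "offering a £500 payment to all schools with an additional £1,000 for those allocated to the intervention group". The reason given for the extra amount is "reflecting the greater research load on such schools".
- Phase 1: Adaptation lists, among the questions for the online survey of schools, "how much would English primary schools be prepared to pay for an effective bullying prevention intervention".
- Economic evaluation data collection says that costing will cover "resources used by trainers, Place2Be and schools".

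**The concern.** The first two statements concern the same trial and the same bill, and they cannot both be true. The commitment that follows the first one makes this more than a slip of wording. It promises an assessment of a funding model, and its use of *remain* presumes that schools are already paying under that model. If outside sources pay, the pilot contains no instance of the arrangement it is said to assess.

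What is at stake is how the pilot is read when phase III is considered. The funder decides on progression, informed by the steering committee. A reader of the dissemination section would conclude that schools had joined and stayed while funding the intervention themselves. Under the cost line they would have joined and stayed while someone else funded it. The protocol itself treats money as a driver of participation: it regards payment to schools as indispensable under current budget pressure, and it lists adequate funding as a safeguard against failing to recruit.

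**Working it through.** No power or sample-size calculation is involved. The check sets the statements side by side, adds up the sums given, and looks for data that could support the promised assessment.

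**1. Inputs.** Intervention cost: £1,500 per school (cost line). It is given without components, so it cannot be rebuilt. Schools: "The external pilot cluster RCT will occur in six primary schools (four intervention, two control"). Participation payments: £500 to every school and a further £1,000 to each intervention school.

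**2. The two statements compared.**

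| | Cost line | Dissemination section |
|---|---|---|
| Who pays in the pilot | sources outside the schools | the schools |
| Amount given | £1,500 per school | none |
| Who pays in phase III | not stated | the schools |

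The pilot bill is 4 × £1,500 = £6,000. Under the cost line the schools' share is £0. Under the dissemination section, taking *fund* to mean in full, it is £6,000.

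**3. Is there an explanation?** The version table, 1.0 to 1.5, records no change of funding model. Both statements are current text, and nothing is blacked out at either place. The cost line is the more specific, since it gives an amount, a source and the stage it applies to. That suggests the dissemination sentence is the outdated one, but does not prove it.

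**4. Would the pilot collect data on schools paying?**

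- Research questions: none of the nine names school funding. The fifth asks for recruitment and retention rates, and the ninth asks whether economic methods are feasible.
- Progression criteria: none of the seven names school funding.
- Phase 1 survey: it has the only willingness-to-pay item. That item is hypothetical and lies outside the pilot RCT.
- Economic work: it records resources that schools use, including staff time. This shows part of the burden on schools, not whether they would accept a charge.
- Reasons for non-participation are recorded at recruitment. Under the cost line, they come from schools that were not asked to fund the intervention.

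**5. Which pilot results depend on the funding terms?** Criterion 1 (recruitment and randomisation on time) and criterion 2 (schools retained) rest on decisions by schools to join and stay. Who pays can plausibly affect those decisions.

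**6. The participation payments.** Each intervention school receives £500 + £1,000 = £1,500 and each control school £500, in total 4 × £1,500 + 2 × £500 = £7,000. These are research payments and play no part in the contradiction, so they are not netted against the intervention cost.

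**The case against.** The strongest reply is that this is one stray sentence in a dissemination paragraph. No planned pilot analysis, research question or criterion uses it. A fully green result leads only to a recommendation to seek phase III funding, and the final phase III design is to be settled in light of the pilot. The commitment is also only to judge whether a model is likely to stay workable, which indirect evidence can inform.

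Much of this stands. No pilot criterion or analysis has to change. But the reply neither reconciles the two statements nor says which evidence is meant, and the sentence places the assessment inside the pilot RCT, whereas the willingness-to-pay item belongs to phase 1.

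A reader might infer four stronger things that the documents do not support.

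- *That the funding question has no data behind it.* The phase 1 item and the school resource data are relevant, though indirect. The exact statement is that the pilot as designed does not test schools paying.
- *That an intervention school's position worsens by £3,000 between pilot and phase III.* This needs a phase III charge of £1,500, which is stated nowhere (the £1,500 is a pilot figure), and it needs participation payments to stop. The protocol's emphasis on the need for payment points the other way.
- *That the pilot reimburses schools or pays them to take the intervention.* The payments to an intervention school happen to equal the intervention cost, but the £500 goes to control schools too and the extra £1,000 is tied to research load.
- *That fidelity and acceptability (criteria 3 and 4) are also distorted.* They rest on recordings, logbooks, observations and teacher and student surveys, and nothing in the documents shows that they depend on who pays.

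**Conclusion.** The contradiction is certain and rests on no assumption. The two sections disagree on who funds the intervention in the pilot, and nothing in the protocol resolves it.

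The consequence is conditional on the cost line being right. In that case the pilot does not test a school-funded model, and criteria 1 and 2 are observed on terms different from those the dissemination section describes for phase III. The size of the difference cannot be given, because no phase III charge is stated. Its effect on recruitment or retention is plausible but not quantifiable from the documents.

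If the dissemination sentence were right instead, schools would be paying in the pilot. The cost line would then be wrong, and the protocol would still name no data item or criterion for the promised assessment.

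The point deserves correction before the pilot is used to support a phase III proposal. It does not undermine the pilot's randomisation, sample or outcomes.

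**What to change.** Reconcile the cost line under Intervention and comparator with the dissemination section. If the cost line stands:

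1. Remove the statement that schools fund the intervention in the pilot.
2. Replace the claim that the pilot will assess this funding model with the evidence that will actually inform it: the phase 1 willingness-to-pay item, and one new question in the interview already planned with one staff member per intervention school. The question should ask whether the school would have joined if it had had to fund the intervention.
3. State that pilot recruitment and retention apply to an externally funded intervention.

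If the dissemination sentence stands instead, correct the cost line and say which pilot data will be used for the assessment.

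The cost is protocol wording and one question in at most four interviews (one in each of four schools). The answers will be hypothetical and will come only from schools that joined, so they supplement the phase 1 item and do not replace a test of schools paying. The downside is a narrower feasibility conclusion: whether schools would take part while funding the intervention stays open for phase III planning.
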